#### **17.4 Subject Privacy**

The Sponsor (or Sponsor's representative) or any designees affirm uphold the subjects confidentiality. The subject will be identified by a unique code only; full names will

be masked before transmission to the Sponsor. The confidentiality of the subject's personal data shall be protected in accordance with appropriate laws and regulations. When any formal presentation or publications of data collected as a direct or indirect result of the study are made, the subject privacy will be protected

### **17.5 Protocol Amendments and Emergency Deviations**

All revisions and/or amendments to this protocol must be approved in writing by the Sponsor and the appropriate IRB/IEC. The Investigator will not make any changes to the conduct of the study or the protocol without first obtaining written approval from the Sponsor and the IRB/IEC, except where necessary to eliminate an apparent immediate hazard to a study subject.

Emergency deviations or modifications may be initiated without Sponsor or IRB/IEC approval or a favorable opinion, only in cases where the deviation or modification is necessary to eliminate or avoid an immediate apparent hazard to subjects. Emergency deviations or modifications must be reported to the Sponsor/CRO and the IRB/IEC immediately or in accordance with applicable regulatory requirements.

### **17.6 Records Retention**

The Investigator/the site must arrange for retention of study records at the study center in accordance with applicable regulations and Sponsor SOPs. The Investigator/site should take measures to prevent accidental or premature destruction of these documents. Documents cannot be destroyed without written Sponsor authorization. The Sponsor will inform the Investigator/the site when the destruction of documents is permitted.

### **17.7 Inspection of Records**

In the event of an inspection, the Investigator agrees to allow the Sponsor, its representative and the regulatory authorities' access to all study records. The Investigator will promptly notify the Sponsor/CRO of all requests to inspect a Sumitomo Dainippon Pharma Co., Ltd.-sponsored study by government agencies and will promptly forward a copy of all such inspection reports.

### **17.8 Publication Policy**

Any formal presentation or publication of data collected as a direct or indirect result of the study will be considered a joint publication by the coordinating investigators or the Investigators and the appropriate personnel of the Sponsor. For multicenter studies, it

is mandatory that the first publication is based on all data obtained from all analyses as stipulated in the protocol. Investigators participating in multicenter studies must agree not to present data gathered individually or by a subgroup of centers before the full, initial publication, unless this has been agreed to by all other Investigators and by the Sponsor.

### **17.9 Compensation**

If subjects have any adverse event or injury directly resulting from the study medications or procedures, the Sponsor will appropriately compensate in accordance with applicable regulatory requirements.

PANSS	Positive and Negative Syndrome Scale

Statistical Analysis Plan

Version: 2

Study No. D4904020

PD	Protocol Deviation
PK	Pharmacokinetic
PLCB	Placebo
PP	Per-Protocol
PT	Preferred Term
QC	Quality Control
QTc	QT interval corrected for heart rate
SAE	Serious Adverse Event
SAP	Statistical Analysis Plan
SAS	Statistical Analysis Software
SBP	Systolic Blood Pressure
SD	Standard Deviation
SE	Standard Error
SI	International System of Units
SOC	System Organ Class
TEAE	Treatment Emergent AE
TFL	Tables, Figures and Listings
ULN	Upper Limit of Normal
WBC	White Blood Cell
WHO	World Health Organisation
γ -GTP	γ -Glutamyltranspeptidase

1 SOURCE DOCUMENTS

The Statistical Analysis Plan (SAP) was written based on the following documentation:

Document	Date	Version
Protocol	02-February-2017	2.02
eCRF	10-November-2014	2.0

2 PROTOCOL DETAILS

2.1 Study Objectives

Primary:

The primary objective of the study is to evaluate the efficacy of DSP-5423P (40 and 80 mg/day) compared with placebo in patients with schizophrenia by assessing the mean change in Positive and Negative Syndrome Scale (PANSS) total score from baseline at Week 6.

Secondary:

The secondary objectives are to evaluate the safety of DSP-5423P compared with placebo for 6-week treatment, the long-term safety and efficacy of DSP-5423P, and the pharmacokinetics of DSP-5423P in patients with schizophrenia.

[figure not shown]
2.2 Overall Study Design

This study has two main phases:

1. Double-blind treatment phase: Multicenter, randomized, double-blind, placebo-controlled, parallel-group design
2. Open-label treatment phase: Multicenter, open-label, flexible dose design

The flowchart for this study is given in Figure 1.

Figure 1: Study Flowchart

The study consists of 4 phases: the washout phase, the double-blind treatment phase, the Open-label treatment phase, and the follow-up phase.

In the washout phase, placebo will be applied once daily for 1 week (at least 3 days) in a single-blind manner. After the washout phase, subjects will be randomized to one of three treatments: 40 mg of DSP-5423P, 80 mg of DSP-5423P, and placebo, at 1:1:1 ratio in the Double-blind treatment phase. The study drugs will be applied once daily for 6 weeks. Subjects who completed the double-blind treatment phase can enter the Open-label treatment phase. In the open-label treatment phase, DSP-5423P will be applied as flexible dose (40, 60, or 80 mg) once daily for 28 weeks (outside Japan) or 52 weeks (in Japan).

Subjects who completed the open-label treatment phase or who prematurely discontinued the study drug after entering the double-blind treatment phase will undergo the follow-up assessments in 1 to 2 weeks after the termination of the study drug.

2.3 Sample Size and Power

Double-blind treatment phase:

The target number of randomized subjects is 501.

DSP-5423P 40 mg group 167

DSP-5423P 80 mg group 167

Placebo group 167

The sample size for the study was determined by a Monte-Carlo simulation using Statistical Analysis Software (SAS Version 9.3, SAS Institute). The sample size calculation was based on the number of subjects required for the primary analysis in the modified intention-to-treat (mITT) population, where the primary analysis is to be performed on the change in PANSS total score from baseline at Week 6. The Hochberg procedure will be utilized to adjust multiple comparisons between each DSP-5423P (40 and 80 mg/day) group and the placebo group.

Based on the results of a previous double-blind placebo control study using DSP-5423 (1), the effect size was estimated to be 0.650 for DSP-5423 5 mg/day and 0.667 for DSP-5423 10 mg/day. It is expected that changes in PANSS total score will be smaller in the current study. This is due to patients with new exacerbated psychotic state will be enrolled as opposed to only patients hospitalized within two weeks from acute aggravation of schizophrenia in the earlier study. In addition, the drug-placebo differences in schizophrenia have been documented to decrease over time (2). For the reasons noted above, the effect size in the current study is assumed to be 0.45 which is about two-thirds of the effect size of DSP-5423 5 mg/day and DSP-5423 10 mg/day. A sample size of 133 per group was estimated to yield a complete power (probability of rejecting 2 null hypotheses) of 89% with a two-sided 5% significance level using the Hochberg procedure for multiplicity adjustment for two comparisons and taking an interim analysis for futility into consideration. Considering that there is the possibility

of subjects discontinuing before completion of the double-blind treatment phase, the total sample size will need to be 501 subjects or 167 subjects per treatment group.

3 EFFICACY AND SAFETY VARIABLES

3.1 Primary Efficacy Endpoint(s)

Mean change in PANSS total scores from baseline at Week 6, testing superiority of DSP-5423P (40 or 80 mg/day) over placebo.

3.2 Secondary Efficacy Endpoints

- Mean change in PANSS subscale scores (positive, negative, and general psychopathology) from baseline at Week 6
- Mean change in PANSS five-factor model scores (3) from baseline at Week 6
- Mean change in Clinical Global Impressions – Severity of Illness (CGI-S) score from baseline at Week 6
- Mean change in PANSS total score from the last evaluation before the initial application of DSP-5423P at each visit
- Mean change in PANSS subscales (positive, negative, and general psychopathology) from the last evaluation before the initial application of DSP-5423P at each visit
- Mean change in PANSS five-factor models from the last evaluation before the initial application of DSP-5423P at each visit
- Proportion of subjects who achieve a response, defined as 20% or greater improvement from baseline in PANSS total score at Week 6
- Mean change in CGI-S score from the last evaluation before the initial application of DSP-5423P at each visit
- Time to treatment discontinuation from initial application in the open-label treatment phase

3.3 Safety Variables

- Adverse events (AEs) and adverse drug reactions (ADRs)
- Extrapyramidal AEs and ADRs
- Skin-related AEs and ADRs at the application site
- Assessment of skin irritation reaction at the application site
- Mean change in Drug-Induced Extrapyramidal Symptoms Scale (DIEPSS) total score (excluding overall severity) from baseline at Week 6
- Mean change in individual DIEPSS scores from baseline at Week 6
- Mean change in DIEPSS total score (excluding overall severity) from the last evaluation before the initial application of DSP-5423P at each visit

- Mean change in individual DIEPSS scores (excluding overall severity) from the last evaluation before the initial application of DSP-5423P at each visit
- Serum prolactin concentration
- Electrocardiogram (ECG) parameters (QTc)
- Concomitant use of antiparkinson drugs
- Assessment of suicide using Columbia-Suicide Severity Rating Scale (C-SSRS)
- Laboratory test values, vital signs, and body weight

4 PHARMACOKINETIC/PHARMACODYNAMIC VARIABLES

- Plasma concentrations of blonanserin
- Plasma concentrations of metabolite M-1 (N-de-ethylated metabolite).

5 ANALYSIS POPULATIONS

Analysis populations for the double-blind treatment phase will be determined by blinded data review meeting(s) before the database lock for the double blind treatment phase. Analysis populations for the open-label treatment phase and the DSP-5423P treatment period will also be determined prior to the initial statistical analysis for the open-label treatment phase.

5.1 Modified intention-to-treat population (mITT population)

The mITT population will consist of all subjects who meet all the following:

- Subjects who are randomized and apply the study drug at least once in the double-blind treatment phase.
- Subjects who have baseline and at least one post-baseline PANSS total score rated in the double-blind treatment phase.

5.2 Per-protocol population (PP population)

The PP population will consist of subjects of the mITT population who meet all the following:

- Subjects who meet the inclusion criteria at screening (1) to (4), and (7) and do not meet any of the exclusion criteria at screening (12) to (17), and (22)
- Subjects who meet all of the inclusion criteria at randomization and do not meet the exclusion criterion at randomization (1)
- Subjects who apply at least 80% of the study treatment in the double-blind treatment phase
- Subjects who receive no antipsychotics during the washout phase and the double-blind treatment phase

- Subjects who have no other important protocol deviations with an impact on the efficacy analyses as determined by a blinded data review

5.3 Open-label population

The open-label population will consist of all subjects who apply DSP-5423P at least once in the open-label treatment phase.

5.4 Safety population

The safety population will consist of all subjects who are randomized and apply the study drug at least once during the study.

5.5 DSP-5423P dosed population

The DSP-5423P dosed population will consist of all subjects who apply DSP-5423P at least once during the study. It does not include placebo group subjects who did not apply any DSP-5423P in the open-label treatment phase.

5.6 Pharmacokinetic analysis population (PK population)

The PK population will consist of all subjects who meet all the following:

- Subjects who are randomized and apply DSP-5423P at least once during the study
- Subjects who have at least one plasma concentration of blonanserin after application of DSP-5423P

5.7 Special Subpopulations

Not applicable.

6 DATA HANDLING

6.1 Day 1

Day 1 is defined as the day of the initial application in the double-blind treatment phase. Relative days after Day 1 are calculated as (date of assessment date – date of Day 1) + 1. Relative days prior to Day 1 are calculated as (date of assessment – date of Day 1). The day before Day 1 is Day -1.

Day 1 is also referred as the initial application date of double-blind treatment phase. The day of final application in the double-blind treatment phase will be referred as the final application date of double-blind treatment phase.

6.2 On-treatment Day 1

On-treatment Day 1 is defined as the day of the initial application of DSP-5423P in this study. Relative days after On-treatment Day 1 are calculated as (date of assessment date – date of On-treatment day 1) + 1. Relative days prior to On-treatment Day 1 are calculated as (date of assessment – date of On-treatment Day 1). The day before On-treatment Day 1 is On-treatment Day -1.

On-treatment Day 1 is also referred as the initial application date of DSP-5423P treatment period. The day of final application of DSP-5423P will be referred as the final application date of DSP-5423P treatment period.

Note that "On-treatment day X" is the same as "Day X" in the 40 mg and 80 mg group. For the placebo group however, "On-treatment day 1" is the first day of receiving an active treatment in the open-label treatment phase and "Day 1" is the first day in the double-blind treatment phase. In general, "Day X" is used for analysis for the double-blind treatment phase. "On-treatment day X" is used for analysis for the DSP-5423P treatment period and specifically excluded the double-blind treatment phase data: for subjects in the placebo group.

6.3 Analysis visits, baseline, and post-baseline measures

All data will be organized and analyzed according to the scheduled timing as outlined in Table 4 to Table 6 Schedule of Assessments and according to the visit denoted in the CRFs. Unscheduled visits may be used if scheduled visits are not available, as specified below. The data collected at the discontinuation visit within 7 days from the final application of study drug will be mapped to the next scheduled visit of the actual discontinuation date, as specified below.

Follow to assign analysis visit;

1. Decide post-base line measures,
2. Assign scheduled visit denoted in the CRFs,
3. Assign CRF discontinuation visits,
4. Assign CRF unscheduled visits, when applicable.

A. Double-blind treatment phase

(i) Baseline analysis visit

Defined as the last non-missing data of CRF Screening or CRF Day 1 (Baseline) visit on or before Day 1. Unscheduled visits will not be used.

Statistical Analysis Plan

Version: 2

Study No. D4904020

(ii) Post-baseline data

Defined as the non-missing data on Day 1 through 7 days after the final application of study drug except for Screening and Day 1 (Baseline) visit. Data assessed on Day 1 and captured in the CRF visits of Week 1, discontinuation, and unscheduled visits will be considered as post-baseline data. Data assessed on Day 1 and captured in the CRF visits of Screening and Day 1 (Baseline) will NOT be considered as post-baseline data.

(iii) Post-baseline analysis visit

The post-baseline data will be mapped to post-baseline analysis visits, ie, Week 1, 2, 4, and 6 as follows:

- (1) CRF Week 1, 2, 4, and 6 will be mapped to the corresponding analysis visits, regardless of the actual day of assessment.
- (2) CRF discontinuation visits will be mapped to the earliest missing analysis visit based on the relative day of assessment as follows:

Assessments and tests	Relative Day	Analysis Visit
PANSS, CGI-S, DIEPSS, C-SSRS, Skin irritation assessment, Body weight, Vital signs	Day 1 to 11	Week 1, 2, 4, 6
	Day 12 to 25	Week 2, 4, 6
	Day 26 to 39	Week 4, 6
	Day 40 or later	Week 6
12-lead ECG, Pharmacokinetic	Day 1 to 11	Week 1, 2, 6
	Day 12 to 25	Week 2, 6
	Day 26 or later	Week 6
Laboratory test	Day 1 to 25	Week 2, 6
	Day 26 or later	Week 6

Note: non-missing analysis visits will not be replaced.

- (3) CRF unscheduled visits will be mapped to the earliest missing analysis visit based on the relative day of assessment as follows:

Assessment and tests	Relative Day	Analysis Visit
PANSS, CGI-S, DIEPSS, C-SSRS, Skin irritation assessment, Body weight, Vital signs	Day 1 to 11	Week 1
	Day 12 to 25	Week 2
	Day 26 to 39	Week 4
	Day 40 or later	Week 6
12-lead ECG, Pharmacokinetic	Day 1 to 11	Week 1
	Day 12 to 25	Week 2
	Day 26 or later	Week 6
Laboratory test	Day 1 to 25	Week 2
	Day 26 or later	Week 6

If more than one unscheduled visits satisfy the condition, the earliest one

Statistical Analysis Plan

Version: 2

Study No. D4904020

will be mapped to the analysis visit

Note: non-missing analysis visits will not be replaced.

B. DSP-5423P treatment period

(i) On-Treatment Baseline analysis visit

(1) 40 and 80 mg group in the double-blind treatment phase

Same as the Baseline analysis visit for the double-blind treatment phase.

(2) Placebo group in the double-blind treatment phase

Defined as the last non-missing data in the double-blind treatment phase including unscheduled visits assessed on or before the On-treatment Day 1.

(ii) Post-baseline data

(1) 40 and 80 mg group in the double-blind treatment phase

Defined as the non-missing data on 'On-treatment Day 1' through 7 days after the final application of DSP-5423P, except for Screening and Day 1 (Baseline) visit.

(2) Placebo group in the double-blind treatment phase

Defined as the non-missing data on a day after 'On-treatment Day 1' through 7 days after the final application of DSP-5423P.

(iii) Post-baseline analysis visit for the 40 and 80 mg group

The post-baseline data will be mapped to post-baseline analysis visits, ie, On-treatment Week 1, 2, 4, 6, 7, 8, 10, 14, 18, 22, 26, 30, 34, 42, 50, and 58 according to the CRF visits as follows. Unscheduled visits of the open-label treatment phase will not be mapped.

(1) Scheduled visits except for the discontinuation visits will be mapped regardless of the actual day of assessment as follows:

CRF Visits	DB W1	DB W2	DB W4	DB W6
Analysis Visits	OnT W1	OnT W2	OnT W4	OnT W6
CRF Visits	OL W1	OL W2	OL W4	OL W8
Analysis Visits	OnT W7	OnT W8	OnT W10	OnT W14
CRF Visits	OL W12	OL W16	OL W20	OL W24
Analysis Visits	OnT W18	OnT W22	OnT W26	OnT W30
CRF Visits	OL W28	OL W36	OL W44	OL W52
Analysis Visits	OnT W34	OnT W42	OnT W50	OnT W58

DB, double-blind; OL, open-label; OnT, on treatment; W, Week

Statistical Analysis Plan

Version: 2

Study No. D4904020

- (2) Discontinuation visits will be mapped to the earliest missing analysis visit based on the relative day of assessment as follows:

✧ PANSS, CGI-S, DIEPSS, C-SSRS, Skin irritation assessment,
Body weight, Vital signs

Relative Day	Analysis Visit
Day 1 to 11	OnT W1, 2, 4, 6
Day 12 to 25	OnT W2, 4, 6
Day 26 to 39	OnT W4, 6
Day 40 or later	OnT W6
OL Day 1 to 11	OnT W7, 8, 10, 14, 18, 22, 26, 30, 34, 42, 50, or 58
OL Day 12 to 25	OnT W8, 10, 14, 18, 22, 26, 30, 34, 42, 50, or 58
OL Day 26 to 49	OnT W10, 14, 18, 22, 26, 30, 34, 42, 50, or 58
OL Day 50 to 77	OnT W14, 18, 22, 26, 30, 34, 42, 50, or 58
OL Day 78 to 105	OnT W18, 22, 26, 30, 34, 42, 50, or 58
OL Day 106 to 133	OnT W22, 26, 30, 34, 42, 50, or 58
OL Day 134 to 161	OnT W26, 30, 34, 42, 50, or 58
OL Day 162 to 189	OnT W30, 34, 42, 50, or 58
OL Day 190 to 238	OnT W34, 42, 50, or 58
OL Day 239 to 294	OnT W42, 50, or 58
OL Day 295 to 350	OnT W50 or 58
OL Day 351 or later	OnT W58

Note: non-missing analysis visits will not be replaced.

✧ 12-lead ECG, Pharmacokinetic

Relative Day	Analysis Visit
Day 1 to 11	OnT W1, 2, 6
Day 12 to 25	OnT W2, 6
Day 26 or later	OnT W6
OL Day 1 to 49	OnT W10, 18, 26, 34, 42, 50, or 58
OL Day 50 to 105	OnT W18, 26, 34, 42, 50, or 58
OL Day 106 to 161	OnT W26, 34, 42, 50, or 58
OL Day 162 to 238	OnT W34, 42, 50, or 58
OL Day 239 to 294	OnT W42, 50, or 58
OL Day 295 to 350	OnT W50 or 58
OL Day 351 or later	OnT W58

Note: non-missing analysis visits will not be replaced.

✧ Laboratory test

Relative Day	Analysis Visit
Day 1 to 25	OnT W2, 6
Day 26 or later	OnT W6
OL Day 1 to 49	OnT W10, 18, 26, 34, 42, 50, or 58
OL Day 50 to 105	OnT W18, 26, 34, 42, 50, or 58
OL Day 106 to 161	OnT W26, 34, 42, 50, or 58

Statistical Analysis Plan

Version: 2

Study No. D4904020

OL Day 162 to 238	OnT W34, 42, 50, or 58
OL Day 239 to 294	OnT W42, 50, or 58
OL Day 295 to 350	OnT W50 or 58
OL Day 351 or later	OnT W58

Note: non-missing analysis visits will not be replaced.

- (3) CRF unscheduled visits in the double-blind phase will be mapped to the earliest missing analysis visit based on the relative day of assessment as follows:

Relative Day	Relative Day	Analysis Visit
PANSS, CGI-S, DIEPSS, C-SSRS, Skin irritation assessment, Body weight, Vital signs	Day 1 to 11	OnT W1
	Day 12 to 25	OnT W2
	Day 26 to 39	OnT W4
	Day 40 or later	OnT W6
12-lead ECG, Pharmacokinetic	Day 1 to 11	OnT W1
	Day 12 to 25	OnT W2
	Day 26 or later	OnT W6
Laboratory test	Day 1 to 25	OnT W2
	Day 26 or later	OnT W6

If more than one unscheduled visits satisfy the condition, the earliest one will be mapped to the analysis visit.

Note: non-missing analysis visits will not be replaced in this step.

- (iv) Post-baseline analysis visit for the placebo group

The post-baseline data will be mapped to post-baseline analysis visits, ie, On Treatment Week 1, 2, 4, 8, 12, 16, 20, 24, 28, 36, 44, and 52 according to the CRF visits as follows. Unscheduled visits of the open-label treatment phase will not be mapped.

- (1) Scheduled visits except for the discontinuation visits will be mapped regardless of the actual day of assessment as follows:

CRF Visits	OL W1	OL W2	OL W4	OL W8
Analysis Visits	OnT W1	OnT W2	OnT W4	OnT W8
CRF Visits	OL W12	OL W16	OL W20	OL W24
Analysis Visits	OnT W12	OnT W16	OnT W20	OnT W24
CRF Visits	OL W28	OL W36	OL W44	OL W52
Analysis Visits	OnT W28	OnT W36	OnT W44	OnT W52

OL, open-label; OnT, on treatment; W, Week

- (2) Discontinuation visits will be mapped to the earliest missing analysis visit based on the relative day of assessment as follows:

Statistical Analysis Plan

Version: 2

Study No. D4904020

- ◇ PANSS, CGI-S, DIEPSS, C-SSRS, Skin irritation assessment,
Body weight, Vital signs

Relative Day	Analysis Visit
OL Day 1 to 11	OnT W1, 2, 4, 8, 12, 16, 20, 24, 28, 36, 44, or 52
OL Day 12 to 25	OnT W2, 4, 8, 12, 16, 20, 24, 28, 36, 44, or 52
OL Day 26 to 49	OnT W4, 8, 12, 16, 20, 24, 28, 36, 44, or 52
OL Day 50 to 77	OnT W8, 12, 16, 20, 24, 28, 36, 44, or 52
OL Day 78 to 105	OnT W12, 16, 20, 24, 28, 36, 44, or 52
OL Day 106 to 133	OnT W16, 20, 24, 28, 36, 44, or 52
OL Day 134 to 161	OnT W20, 24, 28, 36, 44, or 52
OL Day 162 to 189	OnT W24, 28, 36, 44, or 52
OL Day 190 to 238	OnT W28, 36, 44, or 52
OL Day 239 to 294	OnT W36, 44, or 52
OL Day 295 to 350	OnT W44 or 52
OL Day 351 or later	OnT W52

Note: non-missing analysis visits will not be replaced.

- ◇ 12-lead ECG, Laboratory test, Pharmacokinetic

Relative Day	Analysis Visit
OL Day 1 to 49	OnT W4, 12, 20, 28, 36, 44, or 52
OL Day 50 to 105	OnT W12, 20, 28, 36, 44, or 52
OL Day 106 to 161	OnT W 20, 28 36, 44, or 52
OL Day 162 to 238	OnT W28, 36, 44, or 52
OL Day 239 to 294	OnT W36, 44, or 52
OL Day 295 to 350	OnT W44, or 52
OL Day 351 or later	OnT W52

Note: non-missing analysis visits will not be replaced.

C. Open-label treatment phase

For the analysis of open-label treatment phase, analysis visits for all treatment groups are derived using the same algorithm for the placebo group for the DSP-5423P treatment period.

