**Table 4 Schedule of Assessments for outside Japan (Open-label treatment phase)**

	Double-blind treatment phase	Open-label treatment phase (28 weeks)									Discontinuation	Follow-up phase (1-2 weeks)
Visit No.	6	101	102	103	104	105	106	107	108	109	Discontinuation visit	Follow-up visit
Timeline from the beginning of the open-label treatment phase a (Study timeline)	- (Week 6)	Open-Week 1 (Week 7)	Open-Week 2 (Week 8)	Open-Week 4 (Week 10)	Open-Week 8 (Week 14)	Open-Week 12 (Week 18)	Open-Week 16 (Week 22)	Open-Week 20 (Week 26)	Open-Week 24 (Week 30)	Open-Week 28 (Week 34)	-	-
Visit window in the open-label treatment phase (Day)	-	Open-5-11	Open-12-18	Open-26-32	Open-50-64	Open-78-92	Open-106-120	Open-134-148	Open-162-176	Open-190-204	At discontinuation +5 f	6-17 days after completion of treatment or discontinuation e
Hospitalization b	←-----											
Inclusion/ Exclusion criteria assessments	(X)											
Dispense study drug	(X)	X	X	X	X	X	X	X	X	X		
Study treatment compliance	(X)	X	X	X	X	X	X	X	X	X	X	
PANSS	(X)	X	X	X	X	X	X	X	X	X e	X e	
CGI-S	(X)	X	X	X	X	X	X	X	X	X e	X e	
DIEPSS	(X)	X	X	X	X	X	X	X	X	X e	X e	
C-SSRS	(X)	X	X	X	X	X	X	X	X	X e	X e	
Skin irritation assessment	(X)	X	X	X	X	X	X	X	X	X	X	
Laboratory test c	(X)			X		X		X		X e	X e	
Pregnancy test d	(X)									X	X	
12-lead ECG	(X)			X		X		X		X e	X e	
Body weight	(X)	X	X	X	X	X	X	X	X	X	X	
Body temperature, blood pressure, pulse rate	(X)	X	X	X	X	X	X	X	X	X	X	
Adverse event monitoring	←-----											
Blood sampling for PK	(X)									X e	X e	

- a Open-Day 1 is defined as the day of the initial application of the study drug in the open-label treatment phase.
- b All subjects can be inpatients or outpatients.
- c At Visit 109 and at the discontinuation visit, blood samples will be collected under fasting conditions (at least 10 hours after the last meal). At other visits, blood samples should be collected under fasting conditions (at least 10 hours after the last meal) whenever possible.
- d To be performed only in female subjects who are premenopausal and of childbearing potential.
- e Must be performed before the beginning of post-treatment with antipsychotics excluding the study drug.

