- f Discontinuation is defined as the last date of study drug application. The subject will undergo the discontinuation assessments within 5 days since the last date of study drug application.
- g Completion of treatment or discontinuation is defined as the last date of study drug application. The subject will undergo the follow-up assessments in 6 - 17 days since the last date of study drug application.

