**10.4 Inpatient or Outpatient**

All subjects will be hospitalized from screening until Day 14 (Visit 4) in the double-blind treatment phase. After Day 14 and completion of assessments at Visit 4, any subject who meets all the following criteria can be an outpatient.

- The subject has family members or care-givers (eg, a social worker, case worker, nurse) who can aid in applying the study drug to the subject and visit the study center.
- The Investigator considers the subject, whose psychiatric symptoms are stable without safety concerns, can be an outpatient.

During the inpatient/hospitalized period in the double-blind treatment phase, all subjects will be permitted to stay outside of the study center only twice, for 3 days and 2 nights each time, as needed. The subject who are currently hospitalized must return to the study center the day before each scheduled visit. All subjects can be discharged from the study center after the treatment in the double-blind treatment phase and completion of assessments at Visit 6, or after completion of assessments at the discontinuation visit. In the open-label treatment phase, the subjects can be

inpatients or outpatients.

The Investigator will record the dates of hospitalization and discharge in the CRFs.

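### Blood samples for PK taken up to 7 days after the last daily patch can be counted as on-treatment exposure in the by-dose summaries

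*SAP*

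**What the plan says.** Protocol 10.1 has the patches replaced every day. Protocol Tables 4 and 5 schedule a PK sample at the discontinuation visit. On timing, Table 4 states: "The subject will undergo the discontinuation assessments within 5 days since the last date of study drug application". A further footnote to that sample reads: "Must be performed before the beginning of post-treatment with antipsychotics excluding the study drug".

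The general rule in SAP 6.3 is: "The data collected at the discontinuation visit within 7 days from the final application of study drug will be mapped" to a scheduled visit. The section defines double-blind post-baseline data as "non-missing data on Day 1 through 7 days after the final application of study drug", apart from the screening and baseline visits, and makes no exception for PK. It then states: "CRF discontinuation visits will be mapped to the earliest missing analysis visit based on the relative day of assessment as follows". PK shares its rows in that table with the 12-lead ECG. Unscheduled visits have a parallel rule, also with a PK row: "CRF unscheduled visits will be mapped to the earliest missing analysis visit based on the relative day of assessment as follows". For the open-label phase, "analysis visits for all treatment groups are derived using the same algorithm for the placebo group" in the DSP-5423P treatment period.

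SAP 7.8 summarises concentrations at Weeks 1, 2 and 6 by treatment group, and at Weeks 34 and 58 by the latest dose before sampling. It fits geometric-mean ratio models at Weeks 6 and 34. The only values it leaves out are those below the detection limit. The PK population (SAP 5.6) requires one concentration after application and has no timing condition.

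**The concern.** A 7-day window may suit a rating scale. For a drug delivered by a patch changed every 24 hours, it can admit samples taken days after the last patch was due for replacement. Such a sample would still be labelled as 40, 60 or 80 mg/day exposure, and it would pull the geometric mean for that dose down.

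The elderly/non-elderly, sex, country and race ratios are also exposed, but they are biased only if the share or the lag of late samples differs between the groups compared.

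Pharmacokinetics is a stated secondary objective. Protocol 15.3.7 itself defines the by-visit summaries and the elderly/non-elderly ratio, so they are not deferred to the separate PK plan, which covers analyses the protocol does not define. Without a prespecified timing rule, excluding off-patch samples later would be a post hoc choice made with treatment and concentrations known.

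**Working it through.** The plan states no figure on this point, so there is none to reproduce. The check traces where the samples go and then sizes the effect under stated assumptions.

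**Where the samples go (SAP 6.3, PK rows)**

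| Day of discontinuation sample | Mapped to | Summarised in SAP 7.8? |
|---|---|---|
| Double-blind Day 1–11 | earliest missing of Week 1, 2, 6 | yes |
| Double-blind Day 12–25 | earliest missing of Week 2, 6 | yes |
| Double-blind Day 26 or later | Week 6 | yes |
| Open-label Day 1–161 | Open-Week 4, 12 or 20 first | no |
| Open-label Day 162–238 | Open-Week 28 (Week 34), if missing | yes |
| Open-label Day 239–350 | Open-Week 36 or 44 first | no |
| Open-label Day 351 or later | Open-Week 52 (Week 58), if missing | yes |

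For example, a Day 20 sample from a subject with Weeks 1 and 2 present goes to Week 6. All five summarised visits can be reached. Week 6 is the main route.

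**Assumed half-life**

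The only kinetic information is in Protocol 4.2: in healthy adults on an earlier 32 mg patch, steady state was almost attained by 7 days of repeated use. Reading that as a fraction f of 90 to 97% is an assumption. With first-order kinetics, t½ = 7 × ln 2 / (−ln(1 − f)):

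- f = 0.90: 4.852 / 2.303 = 2.11 days
- f = 0.97: 4.852 / 3.507 = 1.38 days

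**Fraction remaining**

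Assume decline starts 24 h after the last application. The fraction left at day D is 2^(−(D − 1)/t½).

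| Days since last application | t½ = 2.11 d | t½ = 1.38 d |
|---|---|---|
| 5 (protocol limit) | 0.268 | 0.135 |
| 7 (SAP limit) | 0.139 | 0.050 |

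**Effect on the geometric mean**

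If lags are uniform on 0 to L days, the mean time beyond the first 24 h is (L − 1)²/(2L). That is 0.25 d for L = 2 (prompt) and 1.6 d for L = 5 (even). The change in the geometric mean is exp(−share × mean days off × ln 2 / t½) − 1.

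| Share of samples | Lags | t½ = 2.11 d | t½ = 1.38 d |
|---|---|---|---|
| 0.10 | prompt | −0.8% | −1.2% |
| 0.10 | even over 0–5 d | −5.1% | −7.7% |
| 0.113 | even over 0–5 d | −5.8% | −8.7% |

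The 0.113 share is illustrative. The plan allows 167 − 133 = 34 drop-outs per group. If half of them (17) supply a Week 6 sample, the share is 17/(133 + 17) = 0.113. The 34 is a planning allowance, not a maximum.

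**Effect on a subgroup ratio**

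The same formula applies, with the difference in share between the two groups.

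- Equal shares and lags: 0%.
- Difference of 0.05, prompt sampling: −0.4% / −0.6%.
- Difference of 0.05, even lags: −2.6% / −3.9%.

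Small groups are more sensitive. If a dose had 10 elderly subjects (an assumption; the documents give no count), one day-5 sample would lower that group's geometric mean by 1 − 0.268^0.1 = 12% to 1 − 0.135^0.1 = 18%.

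Setting below-limit values to missing works the other way, because it removes the most washed-out samples and keeps the partly washed-out ones.

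**The case against.** The strongest case is that the effect is probably small. The protocol asks for the visit within 5 days, so the day-7 figures describe a visit that is already late. The sample must precede any new antipsychotic, and "All subjects will be hospitalized from screening until Day 14 (Visit 4) in the double-blind treatment phase", so many draws should be prompt, and prompt sampling gives only about 1%. The Week 34 and Week 58 routes are narrow, and the second exists only in Japan. The half-life, lags and shares are all assumed. All of this stands, and it limits the size. It does not supply the missing rule, because 5 days is still well beyond a 24 h application interval.

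The SAP also follows Protocol 15.3.8.2, which sets the 7-day window and the discontinuation mapping for all data. That is correct, so the fix is a departure that must be recorded. Listings and the study team's review of PK data give some visibility, but that review settles which subjects belong to the PK population and states no timing criterion for samples.

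Unscheduled PK samples may be rare, since the protocol schedules none. The SAP nevertheless has a row that maps them, so the rule should cover them.

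Two limits of the fix remain. A window counted from application would pass a patch removed early, because only the date of final removal is recorded. It also takes samples selectively from subjects who discontinue. Both appear small, and the samples left out are still reported.

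**Conclusion.** The concern holds. Followed as written, the plan labels samples drawn up to 7 days after the last daily patch as on-treatment exposure at Weeks 1, 2, 6, 34 or 58 whenever that visit is missing and the mapping reaches it, and no later step removes them.

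The missing rule is a matter of text; its size is not known. Under the assumed half-life of 1.4 to 2.1 days, a 10% share lowers the Week 6 geometric mean by about 1% with prompt sampling and by 5 to 8% with lags spread evenly over 0 to 5 days. Bias in the subgroup ratios is zero unless shares or lags differ. No efficacy test uses these data. The change should be made because it is cheap and can be fixed in advance, not because a large distortion has been shown.

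**What to change.** In SAP 6.3 and 7.8, map discontinuation PK samples and unscheduled double-blind PK samples to a scheduled visit only if they were drawn within 28 h of the last application: one 24 h interval plus a 4 h tolerance. Another tolerance of a few hours is acceptable if fixed before unblinding. List or summarise the remaining samples separately. Leave scheduled-visit samples as they are, so that subjects who missed an application are not removed. Record the departure from Protocol 15.3.8.2 in SAP section 8, which currently lists no changes. Report the number of below-limit values by visit and dose.

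Under the same assumptions, a sample retained at exactly 28 h has fallen by 1 − 2^(−(4/24)/t½) = 5.3% to 8.0%. With a 10% share all at 28 h, the geometric mean falls by at most 0.6% to 0.8%.

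The cost is one rule, one entry in section 8 and one count row in the PK tables. Protocol 11.4 already puts the sampling times and the times of the last two applications on the CRF, so no new data are needed. The by-visit summaries lose a few samples, all from subjects who discontinued or had unscheduled draws.
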